of 12 social ecological roles within the village (hereafter: “network positions”) that are relevant to suicide prevention. These network positions include 7 organizational affiliations: individuals interacting with young people on the basis of their position in schools, health care facilities, mental health services, social services, religious institutions, tribal governments, city governments (including law enforcement); and 5 family roles: Elder; parent or *anayakaak*; a sibling or cousin who is close: *aakauraga*; other adult family member who is also a mentor: *ilatka*, or friend. The final “network position” will be “Other”, with an open-ended response. Investigators will recruit all available people within the above-named village institutions, youth (ages 15-24), and others interested in participating. This recruitment is feasible: investigators recruited 75% of eligible village participants within 5 days in two villages in the pilot study. Random sampling is not feasible or required for members of formal organizations. Instead, investigators will perform a census of all individuals in formal network positions, which are limited in number (estimated $n \approx 35$ in each community). The possibility of data missing not-at-random will be assessed using reported demographics of non-responders from among all eligible participants. Random sampling of family roles in the community is hindered by the lack of a network sampling frame that could describe the distribution of ties across the communities. The investigators’ solution is to employ a rigorous respondent referral method to recruit a sample of informal/family respondents for reports on informal networks, supplemented by active solicitation of at least one member from each household in the community. Previous similar efforts in Arctic communities by the study team have shown high levels of representativeness while conforming to non-intrusive, community acceptable standards of research participation. There, recruitment was able to produce data from roughly 85% of all households and a close match to Census averages across a range of demographic categories^{44,143}.

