
Organizational network positions
Village-level:
Tribe staff
Health workers (CHAPs)
Behavioral health workers
School personnel
Social Services workers
Religious leaders
City Government/Law Enforcement
Region-level:
Norton Sound Doctors
CHAP supervisors
School District health counselors

Baseline Steps toward Prevention (STP) Survey:

The Steps toward Prevention (STP) Survey will be administered at baseline (1-2 months before PC CARES implementation) and three months post-intervention. The questionnaire will be self-administered via a touch screen computer interface and will include 1) basic demographic questions, 2) questions about skills, knowledge, and attitudes toward taking preventive actions in their family and community, 3) questions about prevention actions they have done in the past 3 months, as well as permission to contact them again within a year to do a follow-up survey. The computer interface will allow the respondent to answer questions privately and quickly with a touch screen, and press 'enter' so their answers are secured. The Steps toward Prevention Baseline Survey will be open to any village resident aged 15 or older. Everyone filling out a 15-20 minute survey will receive \$20. We will obtain informed consent from all participants on the touch screen computer interface before they proceed to the survey questions. In each village, we expect to administer the Baseline STP Survey to 65-150 people.

Network Positions:
Informal/Community Supporters
Elders (Ana and Taata)
Parents
Sibling (includes youth 15+)
Close cousins and peer family (includes youth 15+)
Adult family (includes close family friends)
Other adults
Friends (includes youth 15+)
Formal/Organizational Supporters
Youth Leaders (includes youth 15+)
Tribal/Community leader
CHAPs
Behavioral Health Aid/TANF/Social Services
Clinic staff
Counselor/Regional Health Provider
Teacher/school staff
Pastor/Religious leader
VPO/VPSO
Kawerak staff

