Recruitment for Steps Toward Prevention Survey: Our pilot research produced a roster of social ecological roles within the village (hereafter: 'network positions') that are relevant to suicide prevention. These positions are listed in boxes to the left. We will recruit all available people within the village institutions (targeted recruitment of individuals holding formal positions), youth (ages 15-24) (set up a table at the school to talk to students about our research), and others in the village interested in participating. We expect that some of those who participate in the Baseline Survey will also participate in the PC CARES intervention and some will not.

Beyond our initial baseline survey recruitment, we will use Respondent Driven Sampling (RDS) to recruit more widely throughout the community. This means that to recruit community members, we will use a peer-referral system that tracks recruitment patterns via referral coupons. RDS involves giving participants 3 coupons that are redeemed for \$5 if the person they recruited completes a survey (up to 3 people). This means that each respondent can receive a stipend of \$20 for completing the STP Baseline Survey, and an additional \$15 for recruiting 3 other people to fill out a survey, for a total \$35 per respondent. The recruitment payment is intentionally set low enough to avoid encouraging coercion on the part of recruiters,

yet its presence provides the recruiter with an incentive to choose among his/her associates those individuals with whom he/she has enough influence such that the receiver will participate in the study, and the recruiter can be assured of getting the recruitment fee.

Since suicide risk is highest for Alaska Native young people, starting from age 15, it is important to understand the social dynamics, help-seeking and help-giving that occur for this age group. Our recruitment for young people to participate in the STP Baseline Survey will start by collaborating with the schools to determine the most effective, least intrusive means for recruiting students to participate. This could include setting up a table in the school lobby after school or during an event such as a basketball tournament to inform students about the STP Baseline Survey and to recruit them to

participate (see recruitment scripts). If interested, we will ask to speak with their parent (if under 18) and will go through an assent and consent process with both the young person and his or her parent.

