We will obtain informed consent from ToF participants before any ToF-related data collection begins. ToF participants have the option to participate in the ToF surveys and interviews or not, without repercussion. Receiving college credit is not tied to whether facilitators fill out these surveys or participate in interviews. They can opt out of answering and still participate in the training and get college credit for their participation in implementing the Learning Circles. We expect that most TOF participants will have already completed the Baseline PC CARES survey described above. Any who consent, but have not already completed the baseline survey, will be given the option to complete the baseline survey at the beginning of the ToF. All consenting participants will complete the Facilitator Post-Training Survey at the end of the ToF week. Additionally, consenting facilitators will be asked to participate in two 45 minute one-on-one interviews with a PC CARES research team member. These will be administered immediately after the training of facilitators and again after all learning circles have been facilitated. Interviews will cover topics related to quality of their training, adequacy of facilitator support, and confidence in facilitating.

Facilitators will need to reach a minimum level of proficiency before facilitating learning circles in their home communities. They will be told that they can opt out of having their data in the study, but that they need to reach a minimum level of proficiency before facilitating PC CARES. To ensure facilitators understand the content, a test of knowledge gains will focus on the content areas in 'What We Know.' Assessment, done at the end of the week-long ToF, will involve a content-focused group quiz. In our pilot study, this method was fun and acceptable to participants, and allowed trainers to clear up any remaining areas of confusion. When piloting this method at the end of our ToF in November 2015, 100% of our 36 participants answered 11 questions correctly, and the remaining 5 questions with mixed results (only about 70% or 25 people answering correctly), have been modified to be clearer to facilitators. Lastly, all ToF participants will demonstrate proficiency by facilitating one learning circle with a ToF trainer present. ToF trainers will assess facilitator fidelity using the tracking assessment.

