After training, continuing virtual support will be offered to cohorts of facilitators monthly in teleconferences where they can check in with each other, hear about the progress each team is making and offer suggestions for addressing problems or issues as they come up.

RHS Cohort facilitators

A cohort of students in the Rural Human Services Certificate Program at University of Alaska-Fairbanks, Kuskokwim campus will fulfill their practicum requirement by facilitating PC CARES Learning Circles in their home communities. Students who consent to participate in the study will complete 3 surveys (Pre-Training, Post-Training, and 6 month Follow Up) with questions that have already been approved by IRB. In addition, we will ask for consent to take field notes during the Facilitator Training and during the monthly Facilitator support calls. These field notes will focus on what kinds of

questions are raised by trainees, what challenges and success they have as facilitators, and other information related to the experience of being a facilitator.

Surveys for Learning Circle Participants:

The PC CARES Learning Circles, in keeping with tribal partners' preferences, will be open to all residents aged 15+, and will take place in public spaces in each village (e.g. tribal building, school, city building). Exclusion criteria includes persons under the age of 15 because the curriculum requires some level of maturity to understand and make use of the information discussed.

Recruitment of Learning Circle Participants: Trained facilitators will recruit PC CARES participants in the villages they live in or serve. This will likely include word-of-mouth recruitment in the schools, churches, tribal offices, public safety offices, and city buildings and CB radio announcements, flyers, and Facebook events. **At schools, tribal offices, health clinics, facilitators will do targeted recruitment of key employees in those organizations (teachers, principals, tribal leaders, health aids). They may also ask for permission to hang a flyer in that organization's building.** Participation in PC CARES will be voluntary but will seek to have a variety of youth and adults. We will target people in the formal and informal network positions mentioned above.

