If a community member attends a PC CARES Learning Circle, but did not complete the demographic and baseline survey, they will be given the opportunity give informed consent, and if they consent, will be given a paper copy of the survey and asked to complete it.

After each Learning Circle, all participants will be asked to complete (on paper) a survey that includes questions about their skills, knowledge and attitudes toward taking preventive action (from baseline survey), plus questions about satisfaction and about intention to use what was learned in the session. Each time they are asked to complete a survey, participants will be given the option of not filling them out without recourse. Whenever participants are asked to fill out a paper survey, they will be given a blank envelope. In order to maintain privacy and confidentiality, when they complete their survey, they can seal it in the envelope before returning their survey to the facilitator. The facilitator will send all surveys in their sealed envelopes to the research team. Each PC CARES participant will receive a \$20 incentive for purchases from the village store or the grocery store in Nome (which will box and send purchases to villages) for completing the 15-20 minute survey.

Audio Recording:

The PC CARES Learning Circles in the villages will be recorded if all the participants give permission for this to be done. The recordings will be transcribed into written scripts and all identifying information for participants will be removed from the word processing files. The session transcripts will be reviewed to analyze the themes that arise from discussion among LC participants, for curriculum fidelity, and to continuously improve the curriculum as each village cohort implements PC CARES.

In order to obtain assent to be recorded, local facilitators will read a script:

If participants agree, an audio recorder is set up and the session is recorded and saved on a thumb drive. The thumb drive is sent to UMass in a self-addressed, stamped envelope along with the paper surveys after the learning circle is finished. If there is 1 'thumbs down' indicating that a participant does not wish to be recorded, we will not record the

session. The transcripts for these sessions do not have names associated with recorded narratives nor do transcripts have a list of attendees. Attendance records for each learning circle are kept separately.

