Because there is limited internet access in the village where Learning Circles will occur, transferring data electronically is not a viable option. All data will be sent to the research team via USPS in Self Addressed Stamped envelopes that we provide.

Each participating facilitator will receive a \$50 incentive for collecting this data (attendance, surveys, audio recordings of Learning Circles) and sending it to UMass. Once the packet of data is received, the project coordinator will send an electronic Amazon gift card to participating facilitators in appreciation of their time.

Steps toward Prevention 3-Month Follow-Up Survey:

Approximately 3 months after the final PC CARES Learning Circle, we will again use the touch screen computer interfaces to collect follow-up data. This survey will be identical to the baseline survey. Again, the Steps toward Prevention 3-Month Follow-Up Survey will be open to all community members aged 15 +, and we will target recruitment to 1) those who completed the Steps toward Prevention Baseline Survey, 2) those who attended at least 1 PC CARES Learning Circle, and 3) those who inhabit specified formal and informal prevention related roles in the community whether or not they participated in PC CARES. Again, we will use Respondent Driven Sampling to recruit throughout the community with each participant receiving \$20 for completing the Steps toward Prevention 3-Month Follow-Up Survey, and up to \$15 for recruiting others to participate. Again, we expect 65-150 participants per village.

PC CARES at School: For the 2021-2022 school year, we will expand our research to include Nome Public Schools, in addition to the Bering Straits school District, and Northwest Arctic Borough School District.

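### Aim 2's pooled pre-post network comparison can be shifted by a change in the share of Learning Circle attendees between rounds, and no pooled estimate holds that share fixed

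*Combined protocol and SAP*

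**What the plan says.** **Baseline round.** The protocol's baseline section says the survey "will be administered at baseline (1-2 months before PC CARES implementation) and three months post-intervention". It is open to any village resident aged 15 or older, with targeting of role holders and youth and peer referral. The recruitment section adds: "We expect that some of those who participate in the Baseline Survey will also participate in the PC CARES intervention and some will not".

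**Follow-up round.** The 3-Month Follow-Up section sets out to "target recruitment to 1) those who completed the Steps toward Prevention Baseline Survey, 2) those who attended at least 1 PC CARES Learning Circle". Its third target is people in specified formal and informal roles. It continues: "Again, we will use Respondent Driven Sampling to recruit throughout the community". Each round expects 65-150 people per village.

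**Overlap between the survey and the intervention.** On Learning Circle recruitment the protocol says: "We will target people in the formal and informal network positions mentioned above". Consenting facilitators without a baseline "will be given the option to complete the baseline survey at the beginning of the ToF". Attendees without one, if they consent, "will be given a paper copy of the survey and asked to complete it".

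**Analysis.** In SAP Aim 2, 'Recruitment, sample and process', all attendees (about 50 per village) are to be recruited. Respondent numbers are to be similar by network position at both stages. Weights use the Census, homophily and degree, and they correct each person's reported ties. In 'Social network analysis', an edge is the weighted total of people reporting contact with a position. The pre and post structures are compared against a null model to judge the significance of change that is attributed to the intervention. Section D describes many attendees as a self-selected minority already doing the promoted behaviours.

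**The concern.** Before the intervention, attendees cannot be a recruitment target. Afterwards they are a named one. If attendees were already more active and form a different share of respondents in the two rounds, the pooled graph changes even if no individual does. The planned test would credit that change to the intervention, and SAP Section A confirms there is no comparison group that could expose it.

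The SAP accepts that the comparison depends on similar composition, but sets that condition on network position only. No pooled estimate is specified that holds the attendee share fixed or uses only people surveyed in both rounds. It is also not stated whether the facilitator and paper baselines enter the pre-intervention graph.

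**Working it through.** **1. The plan's own sample size.** The midpoint of 65-150 is 107.5 (stated: 108). 3 x 108 = 324 per cohort, and 9 x 108 = 972 against the stated figure of about 975. These reproduce.

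The attendee share cannot be derived from the plan. The listed groups (14-35 formal, 30-60 youth, 20-40 other) sum to 64-135. With 50 attendees and no overlap they sum to 114-185. Neither is 65-150, and the overlap is not given.

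**2. Formula.** With no individual change:

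shift = (50r/108 - p) x gap

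Here p is the attendee share at baseline and r is the fraction of the 50 attendees who respond at follow-up. The formula holds follow-up at 108, so each missing attendee is replaced by a non-attendee.

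**3. Inputs.**
- Gap: SAP Section E, Table 3 has 19 rows. The attendee minus non-attendee differences sum to 465.3 points (mean 24.5, range 10.3-45.9). They are post-intervention, from people with 2+ sessions, and every row has p<0.05, so they probably overstate the pre-existing gap.
- Diluted gap: 465.3/39 = 11.9. This assumes that the 19 rows are among the 39 behaviour items in Section D and that the other 20 have no gap.
- r: 50% (target) and 65% (pilot) are borrowed from the Aim 1 follow-up survey; 100% is the stated intention. The follow-up shares are 23.1%, 30.1% and 46.3%.
- p: not given; 10-40% is assumed.

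**4. Result, in percentage points** (gap 24.5; diluted gap in brackets):

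| r | p = 10% | p = 20% | p = 30% | p = 40% |
|---|---|---|---|---|
| 50% | +3.2 (+1.6) | +0.8 (+0.4) | -1.7 (-0.8) | -4.1 (-2.0) |
| 65% | +4.9 (+2.4) | +2.5 (+1.2) | 0.0 (0.0) | -2.4 (-1.2) |
| 100% | +8.9 (+4.3) | +6.4 (+3.1) | +4.0 (+1.9) | +1.5 (+0.8) |

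**5. High baseline coverage.** The SAP reports that "investigators recruited 75% of eligible village participants within 5 days in two villages in the pilot study". If that coverage held for future attendees (an assumption), p = 0.75 x 50/108 = 34.7%. The shifts are then -2.8 / -1.1 / +2.8 (diluted -1.4 / -0.6 / +1.4) for r = 50 / 65 / 100%.

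**6. Counting late baselines.** Take p = 20%: 21.6 attendees, 28.4 missing and 86.4 non-attendees. If all 28.4 return a counted baseline, the share is 50/136.4 = 36.7%. The shifts move from +0.8 / +2.5 / +6.4 to -3.3 / -1.6 / +2.4.

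The negative values come from unequal response. At r = 50%, follow-up holds 108 - 25 = 83 non-attendees, 96% of 86.4. At r = 65% it holds 75.5, or 87%. If both groups respond at the same rate f, the share is 50f/(50f + 86.4f) = 36.7% and the shift is zero.

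**7. Cost of holding the share fixed.** If both rounds are weighted to the same share, the composition term is zero. The Kish design effect for moving share s to t is t²/s + (1-t)²/(1-s). For t between 10% and 40% (assumed):
- Follow-up, worst case s = 46.3%, t = 10%: 1.53, so 108 act like 71.
- Baseline, worst case s = 10%, t = 40%: 2.00, so 108 act like 54.

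**The case against.** The case against has several good parts.

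- **The rounds are linked.** Baseline completers are the first follow-up target, both rounds use role targeting and peer referral, and Learning Circles draw on the same positions. This limits the difference between rounds. It does not equalise the attendee share.
- **The weights correct reported ties.** If the bias works through active people reporting more ties, the degree correction may remove part of it. How much cannot be known from the plan, and attendance is not among the weighting variables.
- **The baseline is meant to come first.** SAP Aim 1 ('Data Collection', 'Survey analysis') places the pre-survey before the first session, and the facilitator baseline falls at the start of training. The intent is therefore stated. The protocol's paper-copy paragraph gives no timing, however, and neither form is assigned to the network's pre-intervention graph.
- **Attendance is analysed elsewhere.** Youth close to participants versus others, the isolation of participants, and the four social axes in Section D all separate people by participation. These stand, but they do not supply a pooled attendance-balanced estimate.
- **The figures are not in the unit of the analysis.** They are percentages taking an action, not block-model ties, and the documents give no pre-intervention gap. This stands in full.

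Two stronger readings are tempting. One is that the pooled change must be biased upward. The documents do not support this, because the offsets may be too small or too large. The other is that counting late baselines in itself reverses the sign. It does not: step 6 shows that unequal response or replacement is also needed.

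**Conclusion.** The concern holds for the pooled pre-post graph. Followed as written, the plan can let a change in who answered appear as change due to the intervention. Network position, Census, homophily and degree adjustments may reduce this, but they do not address attendance directly.

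The size is unknown. Without counted late baselines and with high attendee response, the shift is upward. A negative shift arises only if attendees respond less than others at follow-up or are replaced by non-attendees. The illustrated range of -4.1 to +8.9 points (diluted -2.0 to +4.3) rests on assumed baseline shares, response rates borrowed from another survey, and post-intervention pilot gaps. It is not an estimate of bias in the network results.

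A reader might infer that Aim 2 as a whole is invalid. The documents do not support that, because the contrasts that separate participants from non-participants are not affected in the same way. This is a worthwhile, inexpensive improvement to one analysis.

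**What to change.** 1. Report the attendee share among respondents in each round, by village.
2. State that facilitator and paper baselines count as pre-intervention only if completed before that person's first Learning Circle, and flag the rest.
3. Add a sensitivity analysis of the pooled graph that weights both rounds to the same attendee share. Add attendance (yes/no) as one margin to the existing weights, preferably set to the village share from attendance sheets and Census counts. Do not cross attendance with the 12 positions: 108/(2 x 12) leaves about 4.5 respondents per cell per village.
4. Add a secondary analysis limited to people surveyed in both rounds. It carries attrition selection and moves the target away from the whole community, so it should not be primary.
5. In SAP 'Social network analysis', describe the pooled change as associated with the intervention, not as its result.

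Separately, the protocol's Data Analysis section still calls the design a natural stepped wedge, although SAP Section A concedes that the term was misused. Replace it with: staggered pre-post comparison without a comparison group. This is a labelling point and adds no weight to the concern above.

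The cost is wording, one reporting item and two sensitivity analyses on data already collected. The SAP says participants can be isolated, and the baseline survey asks permission to re-contact. The loss of precision in item 3 is at most the design effects in step 7 under the assumptions given there, for the attendance margin alone.
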